**FIGURE: FOREST PLOT EFS BLADDER PRESERVATION UNIVARIATE COX MODEL**

Table 125: Creatinine clearance and ECOG contingency table, only patients with EFS bladder preservation

Creatinine clearance (mL/min)	< 60 (N=)	≥ 60 (N=)	Total (N=)	p value
ECOG				
0				
1				

1. Fisher's Exact Test for Count Data

Table 126: Creatinine clearance and ECOG contingency table, only patients without EFS bladder preservation

Creatinine clearance (mL/min)	< 60 (N=)	≥ 60 (N=)	Total (N=)	p value
ECOG				
0				
1				

1. Fisher's Exact Test for Count Data

Table 127: EFS bladder preservation multivariate model

Characteristic	Multivariate Cox Regression					Multivariate Cox Regression (Excluding PD-L1)				
	N	Event N	HR 	95% CI 	p-value	N	Event N	HR 	95% CI 	p-value
Sex										
Female										
Male										
T Stage										
T2										
T3/T4										
ECOG										
0										
1										
Non Invasive Cancer										
History										
Yes										
No										
PD-L1 High status										
Low/Negative										
High										

HR = Hazard Ratio, CI = Confidence Interval

## 1.2. EFS (SPECIFIC)

### 1.2.1. AGE

Table 128: EFS (specific) by age

Age at start of treatment	Age < 71 (N=)	Age $\geq$ 71 (N=)	Total (N=)	p value
Event Free Survival specific				
No				
Bladder relapse/Metastases				
Bladder relapse				
Metastases				
Death				
Event Free Survival specific				
Event/Death				
No				

1. Fisher's Exact Test for Count Data

Table 129: Median/mean EFS (specific) by age (estimated by Kaplan-Meier)

	Median (months)	CI 95%	Mean	CI 95%
Age < 71				
Age $\geq$ 71				

Table 130: EFS (specific) by age estimated survival ratio

EFS (specific)	Events (% total N)	Patients at risk	% estimated cumulative survival ratio	CI 95%
Age < 71				
At 6 months				
At 12 months				
At 24 months				
At 36 months				
Age $\geq$ 71				
At 6 months				
At 12 months				
At 24 months				
At 36 months				

**1.2.1.1. FIGURE: EFS (SPECIFIC) VS AGE (ABOVE OR BELOW 71)**

## 1.2.2. GENDER

Table 131: EFS (specific) by gender

Sex	Female (N=)	Male (N=)	Total (N=)	p value
Event Free Survival specific				
No				
Bladder relapse/Metastases				
Bladder relapse				
Metastases				
Death				
Event Free Survival specific				
Event/Death				
No				

1. Fisher's Exact Test for Count Data

Table 132: Median/mean EFS (specific) by gender (estimated by Kaplan-Meier)

	Median (months)	CI 95%	Mean	CI 95%
Female				
Male				

Table 133: EFS (specific) by gender estimated survival ratio

EFS (specific)	Events (%, total N)	Patients at risk	% estimated cumulative survival ratio	CI 95%
Female				
At 6 months				
At 12 months				
At 24 months				
At 36 months				
Male				
At 6 months				
At 12 months				
At 24 months				
At 36 months				

### 1.2.2.1. FIGURE: EFS (SPECIFIC) VS GENDER

### 1.2.3. STAGE: T2 vs. T3/T4

Table 134: EFS (specific) by Stage: T2 vs T3/T4

T Stage	T2 (N=)	T3/T4 (N=)	Total (N=)	p value
Event Free Survival specific				
No				
Bladder relapse/Metastases				
Bladder relapse				
Metastases				
Death				
Event Free Survival specific				
Event/Death				
No				

1. Fisher's Exact Test for Count Data

Table 135: Median/mean EFS (specific) by Stage: T2 vs T3/T4 (estimated by Kaplan-Meier)

	Median (months)	CI 95%	Mean	CI 95%
T2				
T3/T4				

Table 136: EFS (specific) by Stage: T2 vs T3/T4 estimated survival ratio

EFS (specific)	Events (% total N)	Patients at risk	% estimated cumulative survival ratio	CI 95%
T2				
At 6 months				
At 12 months				
At 24 months				
At 36 months				
T3/T4				
At 6 months				
At 12 months				
At 24 months				
At 36 months				

#### 1.2.3.1.

#### FIGURE: EFS (SPECIFIC) VS STAGE: T2 vs T3/T4

### 1.2.4. ECOG: 0 vs. 1

Table 137: EFS (specific) by ECOG: 0 vs. 1

ECOG	0 (N=)	1 (N=)	Total (N=)	p value
Event Free Survival specific				
No				
Bladder relapse/Metastases				
Bladder relapse				
Metastases				
Death				
Event Free Survival specific				
Event/Death				
No				

1. Fisher's Exact Test for Count Data

Table 138: Median/mean EFS (specific) by ECOG: 0 vs. 1 (estimated by Kaplan-Meier)

	Median (months)	CI 95%	Mean	CI 95%
0				
1				

Table 139: EFS (specific) by ECOG: 0 vs. 1 estimated survival ratio

Events (% total N)	Patients at risk	% estimated cumulative survival ratio	CI 95%
0			
At 6 months			
At 12 months			
At 24 months			
At 36 months			
1			
At 6 months			
At 12 months			
At 24 months			
At 36 months			

#### 1.2.4.1.

#### FIGURE: EFS (SPECIFIC) VS ECOG: 0 vs. 1

## 1.2.5. Non INVASIVE CANCER HISTORY: YES vs. No

Table 140: EFS (specific) by Non invasive Cancer History: Yes vs. No

Non Invasive Cancer History	Yes (N=)	No (N=)	Total (N=)	p value
Event Free Survival specific				
No				
Bladder relapse/Metastases				
Bladder relapse				
Metastases				
Death				
Event Free Survival specific				
Event/Death				
No				

1. Fisher's Exact Test for Count Data
2. Pearson's Chi-squared test

Table 141: Median/mean EFS (specific) by Non invasive Cancer History: Yes vs. No (estimated by Kaplan-Meier)

	Median (months)	CI 95%	Mean	CI 95%
Yes				
No				

Table 142: EFS (specific) by Non invasive Cancer History: Yes vs. No estimated survival ratio

EFS (specific)	Events (% total N)	Patients at risk	% estimated cumulative survival ratio	CI 95%
Yes				
At 6 months				
At 12 months				
At 24 months				
At 36 months				
No				
At 6 months				
At 12 months				
At 24 months				
At 36 months				

**1.2.5.1. FIGURE: EFS (SPECIFIC) VS NON INVASIVE CANCER HISTORY: YES  
vs. No**

## 1.2.6.PD-L1: HIGH vs. Low/NEGATIVE

Table 143: EFS (specific) by PD-L1: High vs. Low/Negative

PD-L1 High status	Low/Negative (N=)	High (N=)	Total (N=)	p value
Event Free Survival specific				
No				
Bladder relapse/Metastases				
Bladder relapse				
Metastases				
Death				
Event Free Survival specific				
Event/Death				
No				

1. Fisher's Exact Test for Count Data

Table 144: Median/mean EFS (specific) by PD-L1: High vs. Low/Negative (estimated by Kaplan-Meier)

	Median (months)	CI 95%	Mean	CI 95%
Low/Negative				
High				

Table 145: EFS (specific) by PD-L1: High vs. Low/Negative estimated survival ratio

EFS (specific)	Events (% total N)	Patients at risk	% estimated cumulative survival ratio	CI 95%
Low/Negative				
At 6 months				
At 12 months				
At 24 months				
At 36 months				
High				
At 6 months				
At 12 months				
At 24 months				
At 36 months				

### 1.2.6.1. FIGURE: EFS (SPECIFIC) VS PD-L1: HIGH VS. LOW/NEGATIVE

### 1.2.7. CREATININE CLEARANCE: < 60 vs $\geq$ 60 (mL/min)

Table 146: EFS (specific) by Creatinine clearance: < 60 vs  $\geq$  60 (mL/min)

Creatinine clearance	< 60 (N=)	$\geq$ 60 (N=)	Total (N=)	p value
Event Free Survival specific				
No				
Bladder relapse/Metastases				
Bladder relapse				
Metastases				
Death				
Event Free Survival specific				
Event/Death				
No				

1. Fisher's Exact Test for Count Data

Table 147: Median/mean EFS (specific) by Creatinine clearance: < 60 vs  $\geq$  60 (mL/min) (estimated by Kaplan-Meier)

	Median (months)	CI 95%	Mean	CI 95%
< 60				
$\geq$ 60				

Table 148: EFS (specific) by Creatinine clearance: < 60 vs  $\geq$  60 (mL/min) estimated survival ratio

EFS (specific)	Events (% total N)	Patients at risk	% estimated cumulative survival ratio	CI 95%
< 60				
At 6 months				
At 12 months				
At 24 months				
At 36 months				
$\geq$ 60				
At 6 months				
At 12 months				
At 24 months				
At 36 months				

**1.2.7.1. FIGURE: EFS (SPECIFIC) VS CREATININE CLEARANCE:  $< 60$  vs  $\geq 60$  (ML/MIN)**

### 1.3. EFS (SPECIFIC) UNIVARIATE AND MULTIVARIATE COX MODEL

Table 149: EFS (specific) univariate and multivariate Cox model

Characteristic	Univariate Cox Regression					Multivariate Cox Regression					Multivariate Cox Regression (Excluding PD-L1)				
	N	Event N	HR 	95% CI 	p-value	N	Event N	HR 	95% CI 	p-value	N	Event N	HR 	95% CI 	p-value
Age at start of treatment															
Age < 71															
Age ≥ 71															
Sex															
Female															
Male															
T Stage															
T2															
T3/T4															
ECOG															
0															
1															
Non Invasive Cancer															
History															
Yes															
No															
PD-L1 High status															
Low/Negative															
High															
Creatinine clearance															
< 60															
≥ 60															

HR = Hazard Ratio, CI = Confidence Interval; Wald test

#### 1.3.1.1.

#### FIGURE: FOREST PLOT EFS (SPECIFIC) UNIVARIATE COX MODEL

Table 150: Creatinine clearance and ECOG contingency table, only patients with EFS (specific)

Creatinine clearance (mL/min)	< 60 (N=)	≥ 60 (N=)	Total (N=)	p value
ECOG				
0				
1				

1. Fisher's Exact Test for Count Data

Table 151: Creatinine clearance and ECOG contingency table, only patients without EFS (specific)

Creatinine clearance (mL/min)	< 60 (N=)	≥ 60 (N=)	Total (N=)	p value
ECOG				
0				
1				

1. Fisher's Exact Test for Count Data

## 1.4. PFS

### 1.4.1. AGE

Table 152: PFS by age

Age at start of treatment	Age < 71 (N=)	Age ≥ 71 (N=)	Total (N=)	p value
Progression Free Survival (tumour assessment)				
Alive without PD				
PD (tumour assessment)				
Death				
Progression Free Survival (tumour assessment)				
PD/Death				
Alive				
1. Fisher's Exact Test for Count Data				
2. Pearson's Chi-squared test				

Table 153: Median/mean PFS by age (estimated by Kaplan-Meier)

	Median (months)	CI 95%	Mean	CI 95%
Age < 71				
Age ≥ 71				

Table 154: PFS by age estimated survival ratio

PFS	Events (% total N)	Patients at risk	% estimated cumulative survival ratio	CI 95%
Age < 71				
At 6 months				
At 12 months				
At 24 months				
At 36 months				
Age ≥ 71				
At 6 months				
At 12 months				
At 24 months				
At 36 months				

**1.4.1.1.**

**FIGURE: PFS vs AGE (ABOVE OR BELOW 71)**

## 1.4.2. GENDER

Table 155: PFS by gender

Sex	Female (N=)	Male (N=)	Total (N=)	p value
Progression Free Survival (tumour assessment)				
Alive without PD				
PD (tumour assessment)				
Death				
Progression Free Survival (tumour assessment)				
PD/Death				
Alive				

1. Fisher's Exact Test for Count Data

Table 156: Median/mean PFS by gender (estimated by Kaplan-Meier)

	Median (months)	CI 95%	Mean	CI 95%
Female				
Male				

Table 157: PFS by gender estimated survival ratio

PFS	Events (% total N)	Patients at risk	% estimated cumulative survival ratio	CI 95%
Female				
At 6 months				
At 12 months				
At 24 months				
At 36 months				
Male				
At 6 months				
At 12 months				
At 24 months				
At 36 months				

### 1.4.2.1. FIGURE: PFS vs GENDER

### 1.4.3. STAGE: T2 vs. T3/T4

Table 158: PFS by Stage: T2 vs T3/T4

T Stage	T2 (N=)	T3/T4 (N=)	Total (N=)	p value
Progression Free Survival (tumour assessment)				
Alive without PD				
PD (tumour assessment)				
Death				
Progression Free Survival (tumour assessment)				
PD/Death				
Alive				

1. Fisher's Exact Test for Count Data

Table 159: Median/mean PFS by Stage: T2 vs T3/T4 (estimated by Kaplan-Meier)

	Median (months)	CI 95%	Mean	CI 95%
T2				
T3/T4				

Table 160: PFS by Stage: T2 vs T3/T4 estimated survival ratio

PFS	Events (% total N)	Patients at risk	% estimated cumulative survival ratio	CI 95%
T2				
At 6 months				
At 12 months				
At 24 months				
At 36 months				
T3/T4				
At 6 months				
At 12 months				
At 24 months				
At 36 months				

#### 1.4.3.1.

#### FIGURE: PFS vs STAGE: T2 vs T3/T4

#### 1.4.4. ECOG: 0 vs. 1

Table 161: PFS by ECOG: 0 vs. 1

ECOG	0 (N=)	1 (N=)	Total (N=)	p value
Progression Free Survival (tumour assessment)				
Alive without PD				
PD (tumour assessment)				
Death				
Progression Free Survival (tumour assessment)				
PD/Death				
Alive				

1. Fisher's Exact Test for Count Data

Table 162: Median/mean PFS by ECOG: 0 vs. 1 (estimated by Kaplan-Meier)

	Median (months)	CI 95%	Mean	CI 95%
0				
1				

Table 163: PFS by ECOG: 0 vs. 1 estimated survival ratio

PFS	Events (% total N)	Patients at risk	% estimated cumulative survival ratio	CI 95%
0				
At 6 months				
At 12 months				
At 24 months				
At 36 months				
1				
At 6 months				
At 12 months				
At 24 months				
At 36 months				

#### 1.4.4.1.

#### FIGURE: PFS vs ECOG: 0 vs. 1

### 1.4.5. Non Invasive Cancer History: Yes vs. No

Table 164: PFS by Non invasive Cancer History: Yes vs. No

Non Invasive Cancer History	Yes (N=)	No (N=)	Total (N=)	p value
Progression Free Survival (tumour assessment)				
Alive without PD				
PD (tumour assessment)				
Death				
Progression Free Survival (tumour assessment)				
PD/Death				
Alive				

1. Fisher's Exact Test for Count Data
2. Pearson's Chi-squared test

Table 165: Median/mean PFS by Non invasive Cancer History: Yes vs. No (estimated by Kaplan-Meier)

	Median (months)	CI 95%	Mean	CI 95%
Yes				
No				

Table 166: PFS by Non invasive Cancer History: Yes vs. No estimated survival ratio

PFS	Events (% total N)	Patients at risk	% estimated cumulative survival ratio	CI 95%
Yes				
At 6 months				
At 12 months				
At 24 months				
At 36 months				
No				
At 6 months				
At 12 months				
At 24 months				
At 36 months				

#### 1.4.5.1. FIGURE: PFS vs Non invasive Cancer History: Yes vs. No

### 1.4.6.PD-L1: HIGH vs. Low/NEGATIVE

Table 167: PFS by PD-L1: High vs. Low/Negative

PD-L1 High status	Low/Negative (N=)	High (N=)	Total (N=)	p value
Progression Free Survival (tumour assessment)				
Alive without PD				
PD (tumour assessment)				
Death				
Progression Free Survival (tumour assessment)				
PD/Death				
Alive				

1. Fisher's Exact Test for Count Data

Table 168: Median/mean PFS by PD-L1: High vs. Low/Negative (estimated by Kaplan-Meier)

	Median (months)	CI 95%	Mean	CI 95%
Low/Negative				
High				

Table 169: PFS by PD-L1: High vs. Low/Negative estimated survival ratio

PFS	Events (% total N)	Patients at risk	% estimated cumulative survival ratio	CI 95%
Low/Negative				
At 6 months				
At 12 months				
At 24 months				
At 36 months				
High				
At 6 months				
At 12 months				
At 24 months				
At 36 months				

#### 1.4.6.1.

FIGURE: PFS vs PD-L1: HIGH vs. Low/NEGATIVE

### 1.4.7. CREATININE CLEARANCE: < 60 vs $\geq$ 60 (mL/min)

Table 170: PFS by Creatinine clearance: < 60 vs  $\geq$  60 (mL/min)

Creatinine clearance	< 60 (N=)	$\geq$ 60 (N=)	Total (N=)	p value
Progression Free Survival (tumour assessment)				
Alive without PD				
PD (tumour assessment)				
Death				
Progression Free Survival (tumour assessment)				
PD/Death				
Alive				

1. Fisher's Exact Test for Count Data

Table 171: Median/mean PFS by Creatinine clearance: < 60 vs  $\geq$  60 (mL/min) (estimated by Kaplan-Meier)

	Median (months)	CI 95%	Mean	CI 95%
< 60				
$\geq$ 60				

Table 172: PFS by Creatinine clearance: < 60 vs  $\geq$  60 (mL/min) estimated survival ratio

PFS	Events (% total N)	Patients at risk	% estimated cumulative survival ratio	CI 95%
< 60				
At 6 months				
At 12 months				
At 24 months				
At 36 months				
$\geq$ 60				
At 6 months				
At 12 months				
At 24 months				
At 36 months				

#### 1.4.7.1. FIGURE: PFS vs CREATININE CLEARANCE: < 60 vs $\geq$ 60 (mL/min)

## 1.5. PFS UNIVARIATE AND MULTIVARIATE COX MODEL

Table 173: PFS univariate and multivariate Cox model

Characteristic	Univariate Cox Regression					Multivariate Cox Regression					Multivariate Cox Regression (Excluding PD-L1)				
	N	Event N	HR 	95% CI 	p-value	N	Event N	HR 	95% CI 	p-value	N	Event N	HR 	95% CI 	p-value
Age at start of treatment															
Age < 71															
Age ≥ 71															
Sex															
Female															
Male															
T Stage															
T2															
T3/T4															
ECOG															
0															
1															
Non Invasive Cancer History															
Yes															
No															
PD-L1 High status															
Low/Negative															
High															
Creatinine clearance															
< 60															
≥ 60															

HR = Hazard Ratio, CI = Confidence Interval; Wald test

1.5.1.1.

FIGURE: FOREST PLOT PFS UNIVARIATE COX MODEL

Table 174: Creatinine clearance and ECOG contingency table, only patients with PFS

Creatinine clearance (mL/min)	< 60 (N=)	≥ 60 (N=)	Total (N=)	p value
ECOG				
0				
1				

1. Fisher's Exact Test for Count Data

Table 175: Creatinine clearance and ECOG contingency table, only patients without PFS

Creatinine clearance (mL/min)	< 60 (N=)	≥ 60 (N=)	Total (N=)	p value
ECOG				
0				
1				

1. Fisher's Exact Test for Count Data

## 1.6. OS

### 1.6.1. AGE

Table 176: OS by age

Age at start of treatment	Age < 71 (N=)	Age $\geq$ 71 (N=)	Total (N=)	p value
Status				
Alive at end of trial: Patient's decision				
Alive at end of trial according to protocol				
Death				
Patient status				
Death				
Alive				

1. Fisher's Exact Test for Count Data

Table 177: Median/mean OS by age (estimated by Kaplan-Meier)

	Median (months)	CI 95%	Mean	CI 95%
Age < 71				
Age $\geq$ 71				

Table 178: OS by age estimated survival ratio

OS	Events (% total N)	Patients at risk	% estimated cumulative survival ratio	CI 95%
Age < 71				
At 6 months				
At 12 months				
At 24 months				
At 36 months				
Age $\geq$ 71				
At 6 months				
At 12 months				
At 24 months				
At 36 months				

#### 1.6.1.1.

#### FIGURE: OS vs AGE (ABOVE OR BELOW 71)

## 1.6.2. GENDER

Table 179: OS by gender

Sex	Female (N=)	Male (N=)	Total (N=)	p value
Status				
Alive at end of trial: Patient's decision				
Alive at end of trial according to protocol				
Death				
Patient status				
Death				
Alive				

1. Fisher's Exact Test for Count Data

Table 180: Median/mean OS by gender (estimated by Kaplan-Meier)

	Median (months)	CI 95%	Mean	CI 95%
Female				
Male				

Table 181: OS by gender estimated survival ratio

OS	Events (% total N)	Patients at risk	% estimated cumulative survival ratio	CI 95%
Female				
At 6 months				
At 12 months				
At 24 months				
At 36 months				
Male				
At 6 months				
At 12 months				
At 24 months				
At 36 months				

### 1.6.2.1. FIGURE: OS vs GENDER

### 1.6.3. STAGE: T2 vs. T3/T4

Table 182: OS by Stage: T2 vs T3/T4

T Stage	T2 (N=)	T3/T4 (N=)	Total (N=)	p value
Status				
Alive at end of trial: Patient's decision				
Alive at end of trial according to protocol				
Death				
Patient status				
Death				
Alive				

1. Fisher's Exact Test for Count Data

Table 183: Median/mean OS by Stage: T2 vs T3/T4 (estimated by Kaplan-Meier)

	Median (months)	CI 95%	Mean	CI 95%
T2				
T3/T4				

Table 184: OS by Stage: T2 vs T3/T4 estimated survival ratio

OS	Events (% total N)	Patients at risk	% estimated cumulative survival ratio	CI 95%
T2				
At 6 months				
At 12 months				
At 24 months				
At 36 months				
T3/T4				
At 6 months				
At 12 months				
At 24 months				
At 36 months				

#### 1.6.3.1.

FIGURE: OS vs STAGE: T2 vs T3/T4

### 1.6.4. ECOG: 0 vs. 1

Table 185: OS by ECOG: 0 vs. 1

ECOG Status	0 (N=)	1 (N=)	Total (N=)	p value
Alive at end of trial: Patient's decision				
Alive at end of trial according to protocol				
Death				
Patient status				
Death				
Alive				

1. Fisher's Exact Test for Count Data

Table 186: Median/mean OS by ECOG: 0 vs. 1 (estimated by Kaplan-Meier)

	Median (months)	CI 95%	Mean	CI 95%
0				
1				

Table 187: OS by ECOG: 0 vs. 1 estimated survival ratio

OS	Events (%, total N)	Patients at risk	% estimated cumulative survival ratio	CI 95%
0				
At 6 months				
At 12 months				
At 24 months				
At 36 months				
1				
At 6 months				
At 12 months				
At 24 months				
At 36 months				

#### 1.6.4.1.

#### FIGURE: OS vs ECOG: 0 vs. 1

### 1.6.5. Non Invasive Cancer History: Yes vs. No

Table 188: OS by Non Invasive Cancer History: Yes vs. No

Non Invasive Cancer History	Yes (N=)	No (N=)	Total (N=)	p value
Status				
Alive at end of trial: Patient's decision				
Alive at end of trial according to protocol				
Death				
Patient status				
Death				
Alive				

1. Fisher's Exact Test for Count Data

Table 189: Median/mean OS by Non invasive Cancer History: Yes vs. No (estimated by Kaplan-Meier)

	Median (months)	CI 95%	Mean	CI 95%
Yes				
No				

Table 190: OS by Non invasive Cancer History: Yes vs. No estimated survival ratio

OS	Events (% total N)	Patients at risk	% estimated cumulative survival ratio	CI 95%
Yes				
At 6 months				
At 12 months				
At 24 months				
At 36 months				
No				
At 6 months				
At 12 months				
At 24 months				
At 36 months				

#### 1.6.5.1.

FIGURE: OS vs Non invasive Cancer History: Yes vs. No

## PD-L1: High vs. Low/Negative

Table 191: OS by PD-L1: High vs. Low/Negative

PD-L1 High status	Low/Negative (N=)	High (N=)	Total (N=)	p value
Status				
Alive at end of trial: Patient's decision				
Alive at end of trial according to protocol				
Death				
Patient status				
Death				
Alive				

1. Fisher's Exact Test for Count Data

Table 192: Median/mean OS by PD-L1: High vs. Low/Negative (estimated by Kaplan-Meier)

	Median (months)	CI 95%	Mean	CI 95%
Low/Negative				
High				

Table 193: OS by PD-L1: High vs. Low/Negative estimated survival ratio

OS	Events (% total N)	Patients at risk	% estimated cumulative survival ratio	CI 95%
Low/Negative				
At 6 months				
At 12 months				
At 24 months				
At 36 months				
High				
At 6 months				
At 12 months				
At 24 months				
At 36 months				

### 1.6.5.2.

### FIGURE: OS vs PD-L1: HIGH vs. LOW/NEGATIVE

### 1.6.6. CREATININE CLEARANCE: < 60 vs $\geq$ 60 (mL/min)

Table 194: OS by Creatinine clearance: < 60 vs  $\geq$  60 (mL/min)

Creatinine clearance	< 60 (N=)	$\geq$ 60 (N=)	Total (N=)	p value
Status				
Alive at end of trial: Patient's decision				
Alive at end of trial according to protocol				
Death				
Patient status				
Death				
Alive				

1. Fisher's Exact Test for Count Data

Table 195: Median/mean OS by Creatinine clearance: < 60 vs  $\geq$  60 (mL/min) (estimated by Kaplan-Meier)

	Median (months)	CI 95%	Mean	CI 95%
< 60				
$\geq$ 60				

Table 196: OS by Creatinine clearance: < 60 vs  $\geq$  60 (mL/min) estimated survival ratio

OS	Events (%, total N)	Patients at risk	% estimated cumulative survival ratio	CI 95%
< 60				
At 6 months				
At 12 months				
At 24 months				
At 36 months				
$\geq$ 60				
At 6 months				
At 12 months				
At 24 months				
At 36 months				

#### 1.6.6.1. FIGURE: OS vs CREATININE CLEARANCE: < 60 vs $\geq$ 60 (mL/min)

## 1.7. OS UNIVARIATE AND MULTIVARIATE COX MODEL

Table 197: OS univariate and multivariate Cox model

	Univariate Cox Regression					Multivariate Cox Regression					Multivariate Cox Regression (Excluding PD-L1)				
	N	Event N	HR 	95% CI 	p-value	N	Event N	HR 	95% CI 	p-value	N	Event N	HR 	95% CI 	p-value
Age at start of treatment															
Age < 71															
Age ≥ 71															
Sex															
Female															
Male															
T Stage															
T2															
T3/T4															
ECOG															
0															
1															
Non Invasive Cancer History															
Yes															
No															
PD-L1 High status															
Low/Negative															
High															
Creatinine clearance															
< 60															
≥ 60															

HR = Hazard Ratio, CI = Confidence Interval; Wald test

1.7.1.1.

FIGURE: FOREST PLOT OS UNIVARIATE COX MODEL

## 2. SAFETY ANALYSIS

### 2.1. SAFETY SUMMARY: ALL EVENTS IN OVERALL (SAFETY POPULATION)

Table 198: Safety

	N	%	LL IC 95%	UL IC 95%
SAE	No			
	Yes			
	Total			
SAE related	No			
	Yes			
	Total			
AE relationship to treatment (any treatment)	No			
	Yes			
	Total			
AE Grade $\geq$ 3 related to any treatment	No			
	Yes			
	Total			
AE related to both treatments (Durva-Treme)	No			
	Yes			
	Total			
AE related to all treatments (Durva-Treme-Radiotherapy)	No			
	Yes			
	Total			
Adverse Events Related Durvalumab	No			
	Yes			
	Total			
Adverse Events Related RT	No			
	Yes			
	Total			
Adverse Events Related Tremelimumab	No			
	Yes			
	Total			
AE	Yes			
	Total			
AE Grade $\geq$ 3	No			
	Yes			
	Total			

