### **8.1.1. Screening phase**

Screening procedures will be performed up to 28 days before Day 1 of Week 1, unless otherwise specified. All patients must first read, understand, and sign the IEC-approved ICF before any study-specific screening procedures are performed. After signing the ICF, completing all screening procedures, and being deemed eligible for entry, patients will be enrolled in the study. Procedures that are performed prior to the signing of the ICF and are considered standard of care may be used as screening assessments if they fall within the 28-day screening window.

The following procedures will be performed during the Screening Visit:

- Informed Consent
- Review of eligibility criteria
- Medical history and demographics
- Complete physical exam
- ECOG Performance Status
- Vitals signs, weight and height
- 12-lead ECG (in triplicate [2-5 minutes apart])
- Confirm collection of tumor biopsy
- Review of prior/concomitant medications
- Imaging by CT scan
- Clinical laboratory tests for:

- Clinical chemistry (see Table 4)
- Hematology (see Table 5)
- Urinalysis (see Table 6)
- Coagulation (PT, PTT, INR)
- Serum pregnancy test (for women of childbearing potential only)
- Hepatitis B and C and HIV serologies
- Cystoscopy and random biopsies
- Tumor assessment (CT scan)
- Fresh tumor biopsies collection are optional. This is only for those patients who signed the substudy informed consent.
- Urine samples collection (optional; only for patients included in ICO L'Hospitalet). The first urine in the morning would be collected using a standard testing tube of 50 ml.

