## **10.1. Safety parameters**

### **10.1.1. Definition of adverse events**

An adverse event is the development of an undesirable medical condition (other than progression of the malignancy under evaluation) or the deterioration of a pre-existing medical condition following or during exposure to a pharmaceutical product, whether or not considered causally related to the product. An undesirable medical condition can be symptoms (e.g., nausea, chest pain), signs (e.g., tachycardia, enlarged liver) or the abnormal results of an investigation (e.g., laboratory findings, electrocardiogram). In clinical studies, an AE can include an undesirable medical condition occurring at any time, including run-in or washout periods, even if no study treatment has been administered.

The term AE is used to include both serious and non-serious AEs.

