#### **10.3.1. Study recording period and follow-up for adverse events and serious adverse events**

Adverse events and serious adverse events will be recorded from time of signature of informed consent, throughout the treatment period and including the follow-up period (90 days after the last dose of durvalumab + tremelimumab).

During the study, all AEs and SAEs should be proactively followed up for each patient. Every effort should be made to obtain a resolution for all events, even if the events continue after discontinuation/study completion.

If a patient discontinues from treatment for reasons other than disease progression, and therefore continues to have tumor assessments, drug or procedure-related SAEs must be captured until the patient is considered to have confirmed PD and will have no further tumor assessments.

The investigator is responsible for following all SAEs until resolution, until the patient returns to baseline status, or until the condition has stabilized with the expectation that it will remain chronic, even if this extends beyond study participation.

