#### **10.3.3. A guide to the interpretation of the causality question is found in next section. Relationship to protocol procedures**

The Investigator is also required to provide an assessment of the relationship of SAEs to protocol procedures on the SAE report form. This includes both non-treatment-emergent (i.e., SAEs that occur prior to the administration of IP) and treatment-emergent SAEs. A

protocol-related SAE may occur as a result of a procedure or intervention required during the study (e.g., blood collection). The following guidelines should be used by Investigators to assess the relationship of SAEs to the protocol:

- Protocol related: The event occurred due to a procedure or intervention that was described in the protocol for which there is no alternative etiology present in the patient's medical record.
- Not protocol related: The event is related to an etiology other than the procedure or intervention that was described in the protocol. The alternative etiology must be documented in the study patient's medical record.

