#### **10.3.9. Reporting of serious adverse events**

All SAEs will be reported, whether or not considered causally related to the investigational product, or to the study procedure(s). The reporting period for SAEs is the period immediately following the time that written informed consent is obtained through 90 days after the last dose of durvalumab or until the initiation of alternative anticancer therapy. The investigator and/or Sponsor are responsible for informing the Regulatory Authority of the SAE as per local requirements.

Each AE is to be assessed to determine if it meets the criteria for SAEs. If an SAE occurs, expedited reporting will follow local and international regulations, as appropriate.

The sponsor must inform the AEMPS of any Suspected serious or unexpected serious adverse events (SUSAR) that occur in accordance with the reporting obligations, and will concurrently forward all such reports to AstraZeneca. A copy of the report must be sent by e-mail to AstraZeneca at the time the event is reported to the AEMPS by the sponsor.

\* A cover page should accompany the SAE form indicating the following:

- External Scientific Research (ESR)
- The investigator's name and address
- The trial name/title and AstraZeneca ESR reference number

\* Send SAE report and accompanying cover page by way of Email to

If a non-serious AE becomes serious, the same process described before will be followed.

Serious adverse events that do not require expedited reporting to the AEMPS need to be reported to AstraZeneca preferably using the MedDRA coding language for serious adverse events. This information should be reported on a monthly basis and under no circumstance less frequently than quarterly.

The following reportable events must be submitted to the sponsor within 24 hours (or immediately for death or life-threatening events).

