### 1.1.1. AES

### 1.1.1.1. Most frequent AES

Table 205: Most frequent AEs (related or not to treatment) (at least 3 pts approx.  $\geq 10\%$ )

	N	%	LL IC 95%	UL IC 95%
No				
Sí				
Total				
No				
Sí				
Total				

Table 206: Most frequent AEs (at least 3 pts approx.  $\geq 10\%$ ) according to grade

### 1.1.2. AES GRADE ≥ 3

Table 207: AEs with grade 3 or higher

Adverse Event (CTC)	N (%)
---------------------	-------

Table 208: List of all AEs with grade 3 or higher

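### The all-cause safety rates carry no onset condition, so events between consent and the first dose count in the rates reported for the drug-radiotherapy combination

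*Combined protocol and SAP*

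**What the plan says.** Protocol section 10.3.1 sets the start of collection: "Adverse events and serious adverse events will be recorded from time of signature of informed consent". Section 10.3.9 gives the SAE reporting period as "the period immediately following the time that written informed consent is obtained through 90 days after the last dose of durvalumab", or until alternative anticancer therapy begins. The definitions fit that window. Section 10.1.1 counts adverse events at any time, "including run-in or washout periods, even if no study treatment has been administered", and section 10.1.2 names screening among the phases in which an SAE can occur.

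Section 8.1.1 allows a pre-dose interval: "Screening procedures will be performed up to 28 days before Day 1 of Week 1". Cystoscopy and random biopsies are among the procedures listed there. Section 3.1 places the initial resection, also with random biopsies, before the first infusion.

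The protocol recognises pre-dose events as a class. On relating SAEs to protocol procedures, section 10.3.3 says: "This includes both non-treatment-emergent (i.e., SAEs that occur prior to the administration of IP) and treatment-emergent SAEs". That distinction is used only for the SAE form and reaches no planned table.

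The safety set (protocol 11.1.1, SAP 2.2) is every patient with at least one dose. The SAP safety summary is headed "SAFETY SUMMARY: ALL EVENTS IN OVERALL (SAFETY POPULATION", and Table 205 is titled "Most frequent AEs (related or not to treatment". Neither protocol section 11 nor the SAP defines a treatment-emergent event.

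**The concern.** The secondary safety objective (section 2.2) concerns durvalumab plus tremelimumab with concurrent radiotherapy. An event that began before the first infusion cannot be an effect of any of the three. In a single-arm trial no control group shows how much bleeding, infection or urinary pain the screening procedures cause on their own. Such complications resemble bladder toxicity, so a reader of an all-cause grade 3 or higher or SAE rate could not tell that part of it arose before treatment.

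**Working it through.** **Inputs**
- Denominator: 32 patients (SAP 3.1).
- Start of recording: consent (protocol 10.3.1, 10.3.9). Screening: up to 28 days (8.1.1).
- Listing cut for frequent terms: 3 patients (Tables 201 and 205).
- Number of pre-dose events: not given anywhere.

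**Step 1. Which outputs have a filter?**

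| SAP output | Filtered by relationship | Filtered by onset |
|---|---|---|
| Table 198: SAE, AE, AE grade 3 or higher (3 rows) | No | No |
| Table 198: remaining 8 rows | Yes | No |
| Tables 199-200 (SAEs) | No | No |
| Tables 201-204 (toxicities) | Yes | No |
| Tables 205-208 (AEs) | No | No |

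The relationship filter should remove most pre-dose events, since an investigator has little ground to attribute them to a drug not yet given. One of the eight filtered rows is less secure: the row for related SAEs does not say related to what. Section 10.3.2 treats the causal relationship as implied for SAEs that could be associated with a study procedure, so a pre-dose biopsy SAE might enter that row.

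**Step 2. A patient followed literally (constructed).** Consent day -20; biopsies day -14; grade 3 haematuria with a hospital stay from day -12; first infusion day 1; no later event. The patient is in the safety set because a dose was given. The bleed falls after consent, so it is recorded. It makes the patient a Yes for AE, for AE grade 3 or higher and for SAE, although it preceded all drug and radiotherapy.

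**Step 3. Size per patient.** The plan's own figure is the listing cut, described as roughly 10%: 3/32 = 9.4%, which agrees. One patient whose only qualifying event is pre-dose adds 1/32 = 3.1 points. A term with on-treatment cases in two patients reaches the cut of 3 if one further patient has it only before dosing.

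**Step 4. Illustration.** Assume 6 patients have a qualifying on-treatment event, and that 0 to 3 others have one only before dosing. Exact (Clopper-Pearson) 95% intervals:

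| Pre-dose only | Reported rate | 95% CI |
|---|---|---|
| 0 | 6/32 = 18.8% | 7.2 to 36.4 |
| 1 | 7/32 = 21.9% | 9.3 to 40.0 |
| 2 | 8/32 = 25.0% | 11.5 to 43.4 |
| 3 | 9/32 = 28.1% | 13.7 to 46.7 |

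Starting from 3 on-treatment patients, the rate goes from 9.4% to 12.5%, 15.6% and 18.8%. An onset filter returns each rate to its first value.

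**Step 5. Where it can show.** The shell for the any-AE row of Table 198 has a Yes line and no No line, so that rate may already be 100% and could not rise. The effect then falls on the grade 3 or higher, SAE and term-level rates.

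**The case against.** The strongest reply is that the plan already separates cause. Protocol Table 8 asks for adverse events by grade and by relationship to the drugs and to radiotherapy, and eight of the eleven rows of Table 198 do this. That stands, and it limits the point to the all-cause outputs. A reader might infer that every safety table counts all recorded events, or that the reported radiotherapy toxicity is inflated. The documents do not support either reading: the row for events related to radiotherapy and Tables 201-204 are filtered by attribution.

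Second, both visit schedules (synopsis and section 3.2) mark adverse event assessment from week 1, with nothing under screening, and section 11.2.1 describes safety analysis during and after treatment. This casts doubt on how many pre-dose events would be captured. It does not settle the matter, because 10.3.1 and 10.3.9 state recording from consent expressly. The two conflict, and the SAP takes neither side.

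Third, the resection may precede consent. Section 8.1.1 lets standard-of-care procedures done earlier serve as screening assessments, and complications arising before consent would not be recorded. The protocol also calls the resection part of the treatment (section 3.1), and the synopsis words the safety endpoint in terms of the combined-modality treatment. Reporting resection complications is therefore defensible, but the objective in section 2.2 names only the drugs and radiotherapy, so they belong apart from those rates.

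Fourth, Tables 200 and 208 list SAEs and grade 3 or higher events, so a pre-dose event might be recognised there. The shells do not specify an onset column, and a listing does not correct a rate.

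**Conclusion.** The point holds for the SAE, AE and AE grade 3 or higher rows of Table 198 and for Tables 199-200 and 205-208. As written, they admit events from before the first dose. It rests on recording from consent being the operative rule and on at least one screening procedure, or the resection, following consent in some patients.

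The size cannot be stated beyond 3.1 points per affected patient. A reader might go further. For three doses on schedule, the recording window is at most 28 + 56 + 90 = 174 days, of which 28/174 = 16% precede dosing, and it is tempting to take this as the inflation. The documents do not support that. The 28 days are a maximum, and the step from time to events needs the same event rate before dosing as during dual checkpoint blockade with pelvic radiotherapy. No pre-dose rate is given.

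**What to change.** 1. Add a SAP definition: an event is treatment-emergent if it starts, or worsens from its baseline grade, on or after the first dose of study treatment, up to the end of the recording period. Base the three all-cause rows of Table 198 and Tables 199-200 and 205-208 on it. Applying the same filter to the attributed outputs would be consistent and should change little.
2. List events between consent and first dose separately, by patient.
3. State what the related-SAE row is related to.
4. Reconcile the synopsis and section 3.2 schedules with recording from consent in section 10.3.1.

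The cost is a short SAP definition, one added listing and a filter on dates. Section 10.3 already collects start date and changes in grade, and section 8.2.1 provides baseline grading. The drawback is that the headline rates can only stay the same or fall, so the separate pre-dose listing has to be kept to ensure no event disappears from the report.
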